10.2 Device-Associated Adverse Events

10.2.1 Definition of an unanticipated adverse device effect (UADE) event

A UADE event, as defined by cGCP guidelines, is any SAE, life-threatening problem, or death caused by or associated with a device (or with the process of evaluating a device) if that SAE, problem, or death was not previously identified in nature, severity, or degree of incidence in the investigational plan or application (including a supplementary plan or application), or any other unanticipated, serious, device-associated problem that relates to the rights, safety, or welfare of subjects or operators using the investigational product system or the comparator product system.

10.2.2 Reporting of device-associated adverse events

Any adverse event that results in serious injury or death and any type of unanticipated adverse device effect, regardless of seriousness or severity, must be reported to the Investigator once when site becomes aware of the event. Initial reports may be partial and should be updated as additional information becomes available. All unanticipated adverse device effects and all serious adverse events should be reported to the Investigator's IRB in accordance with the IRB reporting requirements.

SAEs will be reported using an Unanticipated Adverse Device Effects (UADE) form, which serves the dual role of capturing pertinent SAE information per industry guidelines and capturing device information pertinent to medical device standards. Other serious events that affect the rights, safety, or welfare of subjects must also be documented on the UADE form and must be reported immediately to Pelex and to the Investigator's IRB according to that IRB's policies.

All SAEs that occur during the study period, whether considered to be related to the investigational product or not, will be reported within 24 hours of knowledge of the event to the sponsor contact below via an EDC notification.

Although all information required for completion of an SAE report form may not be available within the specified time period, the following minimal initial information should be reported: Subject ID #, Site #, an identifiable reporting source name and contact information (e.g. investigator/study coordinator), which of the 6 SAE criteria identified above resulted in the event being deemed “serious”. IRB reporting requirements may also apply for SAEs.

11 RISK ANALYSIS

11.1 Potential Risks of the Investigational Product and Clinical Investigation

Study device is currently seeking 510(k) approval with the FDA and has been identified as a non-significant risk medical device under FDA regulations and guidance documents, specifically Title 21 CFR 812.2(c). Importantly, subjects will experience no greater risk than that associated with standard pelvic floor muscle training plus biofeedback treatment.

The types of risk associated with Pelex Upp align with those associated with biofeedback devices used for PFMT. These risks are all stated in the consent form.

11.2 Potential Benefits of the Investigational Product and Clinical Investigation

Subjects may benefit from this study through the possible improvement in their stress urinary incontinence symptoms. The benefits of the study will also be to the larger population of patients with stress urinary incontinence who would potentially benefit from a non-invasive device for usage at home in treatment of stress urinary incontinence.

The studies made possible by the data collected in this study are expected to lead to confirmation of the clinical efficacy of biofeedback-augmented PFMT performed at home.

11.3 Minimization of Risks

Although the risk to subjects participating in the study is anticipated to be minimal, the clinician, at his/her discretion, will not collect data from those individuals for whom collection is judged to pose an unusually high risk of physical or mental harm or discomfort.

Participation in this study poses no risk to study personnel other than that normally encountered during standard practice. These risks will be minimized by adherence to the following guidelines:

- Personnel should wear appropriate personal protective equipment to avoid contact of the eyes or skin with hazardous materials or products derived from biological sources.

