Methodology Overview	
This will be a prospective cohort study of women > 18 years of age with symptoms of stress urinary incontinence, recruited via an online recruitment tool.
 
After screening, patients meeting inclusion criteria will be given a study brochure, and then given instructions on how to indicate desire to participate in the study. The patient will then be contacted for study participation, including explanation of study and details and completion of Informed Consent. Participants will then complete a pre-treatment urinary incontinence symptom questionnaire(ICIQ).
 
After completion of the above, the participants will then be given a Pelex Upp study, in addition to educational materials on use of the device, and a treatment schedule. Participants will perform a standardized biofeedback-mediated pelvic floor muscle training program with the study device 10 minutes a day, five times a week for 4 weeks. There will be a mid-study check in to assure all devices are functioning appropriately. At the end of the study, participants will complete a post-treatment urinary incontinence symptom questionnaire(ICIQ).
 
Endpoint of the study will be change in stress urinary incontinence symptoms as measured by the ICIQ. The ICIQ will be collected at 2 time points: before study entry, and at study close.

ABBREVIATIONS

PFMT	Pelvic floor muscle training
SUI	Stress urinary incontinence
OAB	Overactive bladder
UI	Urinary incontinence
PFM	Pelvic floor muscles
US/USA	United States of America

TABLE OF CONTENTS

1	INTRODUCTION	11
2	DESCRIPTION OF THE INVESTIGATIONAL PRODUCT	11
2.1	Overview	11
2.2	Proposed Intended Use Statement	11
3	STUDY OBJECTIVES	11
4	STUDY OVERVIEW	12
4.1	Study Approach	12
4.3	Study Duration.....	13
5	STUDY POPULATION	14
5.1	Sample Size and Target Study Population	14
5.1.1	Sample size	14
5.1.2	Study population	14
5.1.3	Alignment with intended study population.....	14
5.1.4	Alignment with intended use of the device.....	14
5.2	Recruitment Methods	14
5.2.1	Recruitment for Study	14
5.2.2	Duration of study activities.....	14
5.3	Patient Selection	15
6	STUDY MATERIALS	15
6.1	Investigational Product.....	15
6.1.1	Identity of the investigational product and accessories	15
6.1.2	Safety issues.....	16
6.1.3	Handling, storage, accountability.....	16
6.1.4	Required training.....	16
6.1.5	External studies.....	17
6.2	Other Study Materials	17
6.2.1	Materials to be provided by study site.....	17

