5.3 Patient Selection

The eligibility criteria for prospective enrollment of subjects are shown in **Table 1**.

Table 1. Inclusion/Exclusion Criteria for Enrollment of Subjects

Inclusion criteria	Female 18 years of age or older Documented symptoms of predominantly stress urinary incontinence as determined by the ICIQ questionnaire
Exclusion criteria	History of pelvic or lower back surgery Pregnancy or less than 12 months post partum History of physician-supervised PFMT History of Kegel exercises greater than once a month History of prior operative delivery Self-reported history of pelvic organ prolapse stage II or greater
Participant Withdrawal Criteria	Inability to demonstrate correct use of product Inability to devote sufficient time necessary to fulfill study goals Worsening of stress urinary incontinence symptoms

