6 STUDY MATERIALS

6.1 Investigational Product

6.1.1 Identity of the investigational product and accessories

The Pelex Upp is intended to allow a patient to perform biofeedback-augmented PFMT non-invasively and at home. It is comprised of a patient contact interface, a connected handheld device, and disposable sensor arrays. The sensor array is a flexible circuit array holding a pair of sensing electrodes and a reference electrode which are connected to a male connector at one end. The patient contact interface, upon which the user sits after disrobing, has the sensor array embedded along the upper surface. A housing compartment within the patient contact interface will hold signal processing equipment, which will be connected to the sensor array externally via a female connector in the front of the patient contact interface. The signal processing equipment will also be separately connected via a cord on the side of the patient contact interface to the handheld device. The handheld device will have two LED systems, a power switch and battery compartment for housing of the power source. The two LED systems will include a “cadence” LED, which flashes in a pre-set pattern for the user to follow with contractions of their own pelvic floor muscles. It will also include a “response” LED, which allows the user to visualize the contraction of their pelvic floor muscles. The sensor array is disposable, and several replacement sensor arrays will be included, and can be changed at the user’s discretion.

The Pelex Upp is completely non-invasive and made of hypoallergenic, non-latex materials.

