6.1.2 Safety issues

The device under investigation is completely non-invasive, and qualifies as a non-significant risk device based on Title 21 CFR 812.2 (c). Safety issues would include skin abrasions and contact allergic reactions from contact of bare skin with the flexible circuit array, which has a mild adhesive applied to it

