7.2 Study Data

Eligible subjects will be invited to participate in the study on a first-come, first-serve basis. Potential donors must provide informed consent to participate. To be eligible for participation, subjects must be at least 18 years of age.

At the discretion of the Investigator and subject to Pelex requirements, urinary incontinence data will be collected from each eligible subject providing signed informed consent.

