7.2.1 Collection of data

Source data is all information, original records of clinical findings, observations or other activities in a clinical trial necessary for the reconstruction and evaluation of the trial. Source data are contained in source documents. Examples of source documents in this study include medical records, memoranda, evaluation checklists, CRF worksheets, and Data Capture

An Electronic Data Capture (EDC) system using an electronic Case Report Form (eCRF) that is compliant with 21 CFR part 11 is the primary data collection instrument for the study. All data requested on the eCRF should be recorded. The EDC system will only allow for data to be collected based on specified fields. The EDC system also generates an audit trail for any corrected data. All data entered on an eCRF must be traceable to a source document.

eCRFs will be completed for each subject enrolled into the clinical study. The Investigator will review, approve, and electronically sign the completed eCRF for each subject; the Investigator's electronic signature will serve as a testament of the Investigator's responsibility for ensuring that all clinical data entered on the eCRFs are complete, accurate, and authentic.

Subjects will be identified in the EDC by a numeric code used for study purposes. Subjects are not identified by name. Data entry staff are expected to follow data protection practices. All procedures for the handling and analysis of data will be conducted using good computing practices meeting FDA guidelines for the handling and analysis of data for clinical trials.

Information about study subjects will be kept confidential and managed according to the requirements of the Health Insurance Portability and Accountability Act of 1996 (HIPAA). Those regulations require a signed subject authorization informing the subject of the following:

1. What protected health information (PHI) will be collected from subjects in this study;
2. Who will have access to that information and why;
3. Who will use or disclose that information; and
4. The rights of a research subject to revoke their authorization for use of their PHI.

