8 DATA QUALITY ASSURANCE

The study screening questionnaire, pre-study survey, post-use survey, and post-study survey are all forms requiring input from subjects. Pelex will endeavor to use electronic forms of data capture whenever possible. Possible forms of electronic data capture include Google

forms and SurveyMonkey. These forms will be configured such that only [name] has access to the raw information in order to protect patient health information.

While obtaining the informed consent, [name] will ask the subject whether she is able to use electronic data forms. In the event that the subject indicates that she is unable to use electronic data forms, then the study team will include a paper journal in the study package. The study package will be returned to [name] who will be responsible for converting the paper form to an electronic format, anonymizing the electronic version, and archiving or destroying the paper form.

Beyond subject input, the study device are intended to collect physiological parameters and store this data on the device. The data will be salvaged when the study materials are returned to the study team. The device data will only be stored using the anonymous subject identifier. Data stored on the device hardware that is returned to the study team will be recovered by [name] following a protocol that has been established with the primary device manufacturer, Arduino. Anonymized recovered data will be collectively stored in a password protected data server or database. The raw data will be backed up at least once to local storage.

The data will be processed through reproducible measures, such as by writing start-to-finish code. When data processing is complete, this code will be applied to a copy of backed-up raw data to confirm the reproducibility of the analysis and integrity of the raw data.

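### Section 11.3 limits participant risk by not collecting data but does not say that a high-risk woman is kept off the device; separately, Section 7.2 leaves collection of the ICIQ endpoint to the Investigator's discretion

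*Protocol*

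**What the plan says.** **Risk measure.** Section 11.3 of the protocol contains two measures. For participants, the clinician has discretion and "will not collect data from those individuals for whom collection is judged to pose an unusually high risk" of physical or mental harm or discomfort. The other measure, protective equipment, is for study personnel.

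**Named hazards.** Section 6.1.2: "Safety issues would include skin abrasions and contact allergic reactions from contact of bare skin with the flexible circuit array", which carries a mild adhesive. Section 6.1.1: "The patient contact interface, upon which the user sits after disrobing, has the sensor array embedded along the upper surface". The synopsis schedules use at home for "10 minutes a day, five times a week for 4 weeks".

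**Eligibility and withdrawal.** Table 1 in Section 5.3 lists six exclusion criteria (pelvic or back surgery, pregnancy or recent birth, supervised training, regular Kegel exercise, operative delivery, prolapse). It lists three withdrawal criteria: incorrect use, too little time, and "Worsening of stress urinary incontinence symptoms". Section 9.2 enrols all who meet the eligibility criteria, in order of arrival.

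**Outcome data.** Section 7.2: "At the discretion of the Investigator and subject to Pelex requirements, urinary incontinence data will be collected from each eligible subject" who has signed consent. The synopsis makes change in the ICIQ the endpoint and has every participant complete it before and after treatment. Section 7.2.1 requires an eCRF for each enrolled subject and adds: "All data requested on the eCRF should be recorded".

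**The concern.** The section on minimizing risk acts on data, whereas the harms that the protocol names come from contact with the device. Leaving a form blank does not protect skin. If the sentence is meant to keep a vulnerable woman off the array, it does not say so, and no criterion in Table 1 does it instead. Site staff would have no written rule for a volunteer who reports adhesive allergy, or for a participant who develops a rash in the second week.

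The second issue concerns the result. The clause in Section 7.2 gives the Investigator a say in whether urinary incontinence data are collected and names no ground for using it. The study has one arm, no blinding (Section 7.3) and about 5 women, so an omission could be decided with a woman's progress known, and each omission is a large part of the result.

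**Working it through.** The plan gives no figure on this point, so there is none to reproduce. The check sets the sections side by side and adds simple arithmetic.

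**1. Exposure.** From the synopsis: 5 sessions per week × 4 weeks = 20 sessions; 20 × 10 minutes = 200 minutes of scheduled contact per woman. This describes exposure, not risk. The protocol gives no expected rate of skin reaction.

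**2. Coverage by Table 1.** 6 exclusion + 3 withdrawal = 9 criteria. The number that mention adhesive or contact allergy, a skin reaction, or a clinician's judgement of high risk is 0.

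**3. Reading 11.3 with 9.2.**
- If not collecting data means only that, the woman still enrols and uses the device, and the hazard is untouched.
- If it means not enrolling her, it sits badly with Section 9.2, because a woman with adhesive allergy can meet every criterion in Table 1 and is then to be enrolled.
- If it means that she stops using the array, nothing says so, and the withdrawal row of Table 1 has no matching entry.

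On each reading a sentence is missing.

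**4. Other provisions.**
- Hypoallergenic materials (6.1.1) lower the risk but are no rule for an individual.
- Physician evaluation (4.1) could identify a woman at risk, but no action is attached to it.
- Deviations without prior approval (12.5) are for emergencies, which a contact rash would not usually be.
- Withdrawal without prejudice (13.2.1) depends on the woman choosing to leave.
- Early termination (7.4.2) is for the whole study or a site.
- Section 10.1 leaves non-serious events outside the sponsor's data, and 10.2.2 covers device events that are serious or unanticipated. A mild skin reaction, being foreseen in 6.1.2, fits neither route.

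**5. Endpoint data.** Section 7.2 allows discretion; the synopsis and 7.2.1 expect the data from everyone. No text says which prevails. With n = 5, one omission is 1/5 = 20% of the endpoint data and two are 2/5 = 40%.

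**6. Illustration of the effect on the mean.** The protocol gives no ICIQ mean or SD and no likelihood of omission, so this rests on an assumption: independent, normally distributed changes with a common SD.
- Omission unrelated to outcome: expected shift 0.
- Omission of the worst responder of five: the expected extreme lies 1.163 SD from the mean, so the mean of the other four moves favourably by 1.163/4 = 0.29 SD.

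Nothing in the protocol suggests that the worst responder would be the one omitted. The second value shows only what a selective omission could do.

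**The case against.** The strongest defence of Section 11.3 is that the device itself gathers data. Section 8 states: "the study device are intended to collect physiological parameters and store this data on the device". The collection that could physically harm a woman in this study is sitting on the array, since a questionnaire cannot abrade skin. Read that way, the sentence withholds device use from a high-risk woman and is loosely worded rather than aimed at the wrong thing. This is plausible, and it stands as the likely intention. It does not supply the missing words on enrolment and stopping, and Section 9.2 still pulls the other way.

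A second defence is that the device is described as non-significant risk, with hypoallergenic materials and a mild adhesive, that a physician evaluates subjects, and that Section 11.1 refers the risks to the consent form. That form is not at hand and may advise stopping. All of this limits the expected harm and argues for a low grade. A reader might infer that the protocol leaves participants unprotected; these provisions and Table 1 show otherwise. Table 1 is also not said to be exhaustive, so its silence is a gap and not a contradiction.

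A third defence concerns the ICIQ. A reader might infer that Section 11.3, through its reference to mental harm or discomfort, allows the ICIQ to be skipped. The documents do not support that: the trigger is unusually high risk from the collection itself, and nothing suggests that the ICIQ poses it. The room to omit comes from Section 7.2 alone. Even there the discretion is tied to the sponsor's requirements and contradicted elsewhere, so the text is inconsistent rather than a clear licence.

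**Conclusion.** The point holds as two separate drafting faults of low severity.

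- **Safety.** Section 11.3 does not state that a woman judged at unusually high risk is not enrolled or stops using the device. With 0 of 9 criteria in Table 1 on the hazards of 6.1.2, and with 9.2 enrolling all who qualify, known adhesive allergy is not a listed ground for exclusion and a skin reaction is not a listed ground for stopping. The size of the harm cannot be derived; it is probably modest given the device.
- **Endpoint.** Section 7.2 allows discretion over ICIQ data that the synopsis and 7.2.1 require. One omission is 20% of the data. The effect on the mean could be anything from none to about 0.29 SD in expectation if the worst of five were omitted under the normal assumption. The study is exploratory and plans no sample size for significance (9.1), so no formal test is at stake, but the principal objective is still efficacy.

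The conclusion concerns the protocol text only and assumes nothing about what the consent form says.

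**What to change.** 1. **Section 11.3.** Reword so that a woman judged at unusually high risk of harm or discomfort is not enrolled or, if already issued a device, stops using it.
2. **Table 1, Section 5.3.** Add an exclusion for known adhesive or contact allergy or clinician-judged high risk. Add a criterion for stopping device use on a skin reaction to the array, worded so that stopping the device does not end follow-up. Section 9.2 needs no edit, because it already points to the specified criteria.
3. **Section 7.2.** Delete the Investigator's discretion for the ICIQ. State that the closing ICIQ and any device-related skin reaction are sought from every woman issued a device while she consents. Recordings from the array end when device use ends.
4. **Section 10.** Add one line so that device-related skin reactions are collected even when not serious. Limiting it to these leaves the rule in 10.1 for other non-serious events unchanged.

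The cost is one sentence in 11.3, one line in each of two rows of Table 1, one deletion and one added sentence in 7.2, and one line in Section 10. No visits or staff are added. The downside is possibly one fewer woman completing device use.

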12 INVESTIGATOR RESPONSIBILITIES

12.1 Site Qualification and Study Oversight

The PI is responsible for general administration of the study.

Before the study, the PI must:

- Obtain approval to conduct the study from the study site's IRB;
- Sign the Protocol PLX-001 Signature Page him/herself and have all sub-investigators sign the Protocol PLX-001 Signature Page and return it to Pelex;
- Provide financial disclosures to Pelex for themselves and all sub-investigators participating in study conduct, per Title 21CFR 54 (see **Section 12.4** below).

During the study, the PI must ensure that:

- The study is conducted ethically;
- Case report forms (CRFs), including Subject ICFs, are provided with each transfer of data requiring informed consent; and
- All other study forms are completed as instructed by Pelex.

In the case of completion or termination of the study or an Investigator's role in the study, or at Pelex request, all study materials must be returned to Pelex.

